11.6.2 SND Summaries by Final Dose

The summary tables for the SND parameters will be presented separately for the double blind and open label phases by the final dose that the subject received at the end of each phase respectively.

11.7 Agreement between Sleep and Nap Diary and Actigraphy

An analysis will be performed to assess the agreement of the following sleep parameters collected via the Sleep and Nap Diary and actigraphy:

- Total Sleep Time
- Sleep Latency
- Duration of Wake
- Number of Awakenings
- Longest Sleep Duration
- Total Time in Bed
- Number of Responders at baseline, Visit 2 (defined as > 6 hours of continuous sleep and < 0.5 hour sleep latency from light off in 3 out of 5 nights.)

The analysis will use data from Visits 2 and 4. Agreement will be assessed using the methods described by Bland and Altman ([4], [5]). Bland and Altman plots (plotting the difference in the measurements from the two sources versus the average of the measurements from the two sources) will be produced and the 95% limits of agreement calculated.

Example SAS code for the calculation of the limits of agreement is given below:

```
proc mixed data=agree method=type1;  
class subjid;  
model diff=/solution ddfm=sat;  
random subjid;  
ods output CovParms=covparms;  
run;  
  
proc means data=agree noprint;  
var diff;  
output out=meandiff mean=meandiff;  
run;
```

```
data loa;  
  merge meandiff covparms(where=(covparm='SUBJID') rename=(estimate=between))  
covparms(where=(covparm='Residual') rename=(estimate=within));  
  std=sqrt(within+between);  
  upper_loa=meandiff+(1.96*std);  
  lower_loa=meandiff-(1.96*std);  
run;
```

For number of responders, a 2 x 2 table will be presented tabulating responders according to the sleep and nap diary against responders according to actigraphy. Agreement between the sleep and nap diary and actigraphy responders will be summarised using Cohen's kappa statistic. The hypothesis that Cohen's kappa differs from 0 will be tested. A 95% confidence interval for Cohen's kappa will also be presented.

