6.1 INCLUSION CRITERIA

To be eligible for study entry, all patients must satisfy all of the following criteria at screening:

- Must be children 2 to 17.5 years of age at Visit 2 who comply with taking the study drug.
- Must have written informed consent provided by a legal guardian and assent (if needed).
- Must have a documented history of ASD according to or consistent with the ICD-10 or DSM-5/4 criteria, or neurodevelopmental disabilities caused by neurogenetic diseases (SMS, Angelman syndrome, Bourneville's disease [tuberous sclerosis]) as confirmed by case note review showing that diagnosis was reached through assessment by a community pediatrician or pediatric neurologist or other health care professionals experienced in the diagnosis who took into account early developmental history and school records.
- Must have current sleep problems including: a minimum of 3 months of impaired sleep defined as ≤ 6 hours of continuous sleep AND/OR ≥ 0.5 hour sleep latency from light off in 3 out of 5 nights based on parent reports and patient medical history. (The maintenance and latency problems do not necessarily have to be in the same 3 nights of the week.)
- May be on a stable dose of non-excluded medication for 3 months, including anti-epileptics, anti-depressants (selective serotonin reuptake inhibitors [SSRIs]), stimulants, all mood changing drugs and β -blockers. (Only morning administration of β -blockers is allowed since β -blockers at night have the potential to reduce endogenous melatonin levels and might cause disturbed sleep).
- The sleep disturbance is not due to the direct physiological effects of any concomitant medications such as SSRIs, stimulants, etc.

After completing 4 weeks of sleep hygiene training (for those who need it) and 2 weeks of placebo run-in, patients will be eligible to continue the study if they comply with the following:

- Continue to fulfil sleep problem criteria (see Inclusion Criterion 4) based on the completed Sleep and Nap Diary entered into the electronic case report form (eCRF)

- Parents demonstrate compliance in Sleep and Nap Diary completion (5 out of 7 nights). Compliance means that in at least 5 out of 7 nights per week (total of 2 weeks before each scheduled visit) the parents complete the diary pages with all mandatory questions (mandatory questions are marked with an asterisk [*] in [Appendix 1](#)).
- Continue to fulfil all other eligibility criteria

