8.4 Full Analysis Set

Efficacy analyses will be performed on the Full Analysis Subset (FAS), and will include all subjects in the Safety Analysis Set who satisfy all major entry criteria (Inclusion Criteria 1-5) and who have a valid mean TST result recorded for baseline and at least one post-baseline period assessment during the double blind phase. Subjects will be classified according to randomized treatment. This analysis set will be used for all efficacy analyses.

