10.6 Prior and Concomitant Medications

Concomitant medications recorded during the study will be coded using World Health Organization (WHO)-Drug. Details of concomitant medication will be listed.

Concomitant medications will be summarized according to whether they were being taken pre-study (prior medications) and/or during the study (concomitant medication). Prior medications are any that were being taken prior to the first dose of study medication (medication stop date prior to the first dose of study medication). Concomitant medications are any that were being taken on or after the first dose of study medication. If the start and stop dates of the concomitant medications do not clearly define the period during which a medication was taken, it will be assumed to be a concomitant medication.

Concomitant medications will be assigned to the phase they were taken: Double-Blind, first Open-Label, second Open-Label. If a concomitant medication starts or is ongoing between Visit 2 and Visit 4, it will be assigned to the Double-Blind phase. If a concomitant medication starts or is ongoing between Visit 4 + 1 day and Visit 5, it will be assigned to the first Open-Label phase. If a concomitant medication starts or is ongoing between Visit 5 + 1 day and Visit 8, it will be assigned to the second Open-Label phase. If the start and stop dates of the concomitant medications do not clearly define the phase during which a medication was taken, it will be assumed to be taken across all phases.

Prior and concomitant medications will be summarized by Anatomical Therapeutic Chemical (ATC) level 2 term and preferred term.

Details of non-pharmacological concomitant measures will be listed.

11 Efficacy

Subjects will be classified and summarized by randomized treatment. For all efficacy assessments, the baseline values will be calculated as the last recorded value prior to the start of randomized treatment. Change from baseline values will be calculated as the assessment score minus the baseline value. For questionnaires the change from baseline values will be calculated for each item and total/subscale score as applicable.

All summaries and analyses will be performed on the FAS set. The primary efficacy endpoint and select secondary efficacy endpoints will also be analyzed on the PP set. Analyses looking at the impact missing data on the primary efficacy endpoint will also be performed on the All Randomized set.

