Table 14.2.12.5	WHO-5 Well-Being Index Score Change from Baseline Analysis During the Open Label Phase	FAS Set
Table 14.2.13.1	Actigraphy Shift in Time to Bed by Scheduled Visit	FAS Set
Table 14.2.13.2	Number of Responders as per Actigraphy during the Run-In Period	All Enrolled Set
Table 14.2.14.1	SND Total Sleep Time Change from Baseline at 13 Weeks Double Blind – MI Analysis	All Randomized Set
Table 14.2.14.2	SND Sleep Latency Change from Baseline at 13 Weeks Double Blind – MI Analysis	All Randomized Set
Table 14.2.14.3	SND Duration of Wake Change from Baseline at 13 Weeks Double Blind – MI Analysis	All Randomized Set
Table 14.2.14.4	SND Number of Awakenings Change from Baseline at 13 Weeks Double Blind – MI Analysis	All Randomized Set
Table 14.2.14.5	SND Longest Sleep Duration Change from Baseline at 13 Weeks Double Blind – MI Analysis	All Randomized Set
Table 14.2.14.6	SND Total Sleep Time Change from Baseline at 13 Weeks Double Blind – BOCF Analysis	All Randomized Set
Table 14.2.14.7	SND Sleep Latency Change from Baseline at 13 Weeks Double Blind – BOCF Analysis	All Randomized Set
Table 14.2.14.8	SND Duration of Wake Change from Baseline at 13 Weeks Double Blind – BOCF Analysis	All Randomized Set
Table 14.2.14.9	SND Number of Awakenings Change from Baseline at 13 Weeks Double Blind – BOCF Analysis	All Randomized Set
Table 14.2.14.10	SND Longest Sleep Duration Change from Baseline at 13 Weeks Double Blind – BOCF Analysis	All Randomized Set
Table 14.2.14.11	SND Total Sleep Time Change from Baseline at 13 Weeks Double Blind – MMRM Analysis including Geographic Region as a Factor	FAS Set
Table 14.2.14.12	SND Total Sleep Time Change from Baseline at 13 Weeks Double Blind – MMRM Analysis including Center as a Factor	FAS Set
Table 14.2.14.13	SND Total Sleep Time Change from Baseline at 13 Weeks Double Blind – MMRM Analysis including Age as a Factor	FAS Set
Table 14.2.14.14	SND Total Sleep Time Change from Baseline at 13 Weeks Double Blind – MMRM Analysis including Gender as a Factor	FAS Set

Table Number	Table Title	Population
Table 14.2.14.15	SND Total Sleep Time Change from Baseline at 13 Weeks Double Blind – MMRM Analysis including ADHD as a Factor	FAS Set
Table 14.2.14.16	SND Total Sleep Time Change from Baseline at 13 Weeks Double Blind – MMRM Analysis including Autism Type as a Factor	FAS Set
Table 14.2.14.17	SND Total Sleep Time Change from Baseline at 13 Weeks Double Blind – MMRM Analysis including Epilepsy as a Factor	FAS Set

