Table 14.2.17.4	SDQ Total Difficulties Score Change from Baseline at 13 Weeks Double Blind – MMRM Analysis including Prior Clonidine Use as a Factor	FAS Set
Table 14.2.18.1	SND Total Sleep Time and Change from Baseline – Double Blind - Descriptive Statistics by Final Dose	FAS Set
Table 14.2.18.2	SND Sleep Latency and Change from Baseline – Double Blind - Descriptive Statistics by Final Dose	FAS Set
Table 14.2.18.3	SND Duration of Wake and Change from Baseline – Double Blind - Descriptive Statistics by Final Dose	FAS Set
Table 14.2.18.4	SND Number of Awakenings and Change from Baseline – Double Blind - Descriptive Statistics by Final Dose	FAS Set
Table 14.2.18.5	SND Longest Sleep Period and Change from Baseline – Double Blind - Descriptive Statistics by Final Dose	FAS Set
Table 14.2.18.6	SND Total Sleep Time and Change from Baseline – Open Label - Descriptive Statistics by Final Dose	FAS Set
Table 14.2.18.7	SND Sleep Latency and Change from Baseline – Open Label - Descriptive Statistics by Final Dose	FAS Set
Table 14.2.18.8	SND Duration of Wake and Change from Baseline – Open Label - Descriptive Statistics by Final Dose	FAS Set
Table 14.2.18.9	SND Number of Awakenings and Change from Baseline – Open Label - Descriptive Statistics by Final Dose	FAS Set
Table 14.2.18.10	SND Longest Sleep Period and Change from Baseline – Open Label - Descriptive Statistics by Final Dose	FAS Set
Table 14.2.19	Summary of Level of Agreement between Sleep and Nap Diary and Actigraphy Assessment of Responder	FAS Set
Table 14.3.1.1	Summary of Study Drug Exposure	Safety Set
Table 14.3.1.2	Summary of Study Drug Modifications	Safety Set
Table 14.3.1.3	% Compliance by Scheduled Visit	Safety Set
Table 14.3.1.4	Dosage Achieved by Scheduled Visit	Safety Set
Table 14.3.1.5	Number of Dropouts -Chi-Square Test	Safety Set
Table 14.3.2.1	Summary of TESS by Scheduled Visit	Safety Set

Table Number	Table Title	Population
Table 14.3.2.2	Overall Adverse Event Summary: Double Blind Phase	Safety Set
Table 14.3.2.3	Overall Adverse Event Summary: Open Label Phase	Safety Set
Table 14.3.2.4	Treatment Emergent Adverse Events by System Organ Class and Preferred Term: Double Blind Phase	Safety Set
Table 14.3.2.5	Treatment Emergent Adverse Events by System Organ Class and Preferred Term: Open Label Phase	Safety Set
Table 14.3.2.6	Serious Adverse Events by System Organ Class and Preferred Term: Double Blind Phase	Safety Set

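### The Visit 2 responder kappa between diary and actigraphy is planned on the FAS, where eligibility on the same diary has emptied or truncated the diary-responder margin

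*SAP*

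**What the plan says.** SAP 11.7 lists the parameters on which diary and actigraphy are to be compared. Most use Visits 2 and 4, but the responder item is tied to one visit: "Number of Responders at baseline, Visit 2 (defined as > 6 hours of continuous sleep and < 0.5 hour sleep latency from light off". The definition asks for this on three of every five nights. For that item "a 2 x 2 table will be presented tabulating responders according to the sleep and nap diary against responders according to actigraphy". Cohen's kappa and a 95% confidence interval follow, and "The hypothesis that Cohen's kappa differs from 0 will be tested".

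The output is Table 14.2.19, "Summary of Level of Agreement between Sleep and Nap Diary and Actigraphy Assessment of Responder", which SAP 16.1 assigns to the FAS. That agrees with the general rule at the start of SAP Section 11: "All summaries and analyses will be performed on the FAS set". SAP 8.4 says the FAS "will include all subjects in the Safety Analysis Set who satisfy all major entry criteria (Inclusion Criteria 1-5").

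Inclusion Criterion 4 (Protocol 6.1) requires at most 6 hours of continuous sleep and/or at least 0.5 hour of latency in 3 out of 5 nights. After run-in a child must "Continue to fulfil sleep problem criteria (see Inclusion Criterion 4) based on the completed Sleep and Nap Diary". Protocol 8.5 withdraws children who fail this check at Visit 2.

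The SAP also plans Table 14.2.13.2, "Number of Responders as per Actigraphy during the Run-In Period", on the All Enrolled Set.

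**The concern.** The diary that classifies a child as a responder is the diary that decided whether the child could be randomised. It covers the 14 nights before Visit 2, and the Actiwatch is worn over those same nights (Table 5-2, footnote 8). Actigraphy plays no part in eligibility. One margin of the 2 x 2 table is therefore set by the entry rule and the other is free.

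Kappa depends on its margins. If one is emptied or squeezed by selection, a low value need not mean that the two instruments measure differently. The primary endpoint is a parent-reported diary measure, so a kappa near zero in the study report could be taken as evidence about the diary when part of it comes from who was admitted. The SAP does not mention the selection or say how to handle an empty diary-responder row.

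**Working it through.** The plan states no kappa, so there is no figure to reproduce.

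**1. The two definitions, night by night.** A responder night is more than 6 h continuous sleep AND less than 0.5 h latency. A Criterion 4 bad night is at most 6 h AND/OR at least 0.5 h. Each is the negation of the other, so every diary night is exactly one of the two.

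**2. Can one child meet both rules?** Neither document says how 3 out of 5 nights applies to a 14-night window. Protocol 7.3.1 glosses similar wording as three or more nights in each week, but for dose modification. Diary compliance requires at least 5 of 7 nights a week.

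- Both rules as a proportion (at least 60% of nights): at least 60% bad leaves at most 40% good. No overlap.
- Exactly five diaries a week: three bad plus three good needs six nights. No overlap.
- Eligibility weekly, responder as a proportion: with seven diaries a week, at least 3 bad leaves at most 4 good per week, or 8/14 = 57%, below 60%. With six, at most 6/12 = 50%. No overlap.
- Both weekly, with six or seven diaries: 3 + 3 = 6 nights fit. Overlap is possible.

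**3. Kappa with no diary responders.** Let actigraphy find m responders among n children. Observed agreement is po = (n − m)/n. Chance agreement is pe = 0 × m/n + 1 × (n − m)/n = po. So kappa = (po − pe)/(1 − pe) = 0 for any m from 1 to n − 1. If m = 0 it is 0/0, undefined.

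**4. A few ineligible children left in.** Take n = 120, k diary responders admitted in error, and actigraphy agreeing on all of them. With actigraphy finding 12 responders (10%) and k = 1: po = 109/120 = 0.908, pe = (1/120)(12/120) + (119/120)(108/120) = 0.893, kappa = 0.015/0.107 = 0.14. With k = 6: po = 0.95, pe = 0.86, kappa = 0.09/0.14 = 0.64. At a 30% actigraphy rate the ceilings are 0.04 and 0.22.

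**5. Illustration by simulation.** The inputs are assumptions, not document figures: nightly good-sleep probability Beta(2,2), Beta(1,3) or Beta(0.5,0.5) across children; actigraphy agreeing with the diary on 80% or 90% of nights; and a diary check at Visit 1 to approximate the earlier screening. Weekly rules apply in each of the two weeks. The FAS is represented by children who also pass the run-in diary check.

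| Reading | Children entering run-in | FAS |
|---|---|---|
| Proportion of nights, 5 to 7 diaries a week | 0.32-0.71 | 0 |
| Both weekly, 7 diaries | 0.44-0.75 | 0.33-0.64 |
| Both weekly, 6 diaries | 0.39-0.71 | 0.19-0.48 |

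For example, Beta(2,2) with 80% nightly agreement, the weekly reading and seven diaries gives about 0.50 against 0.39, a fall of 0.11/0.50 = 22%.

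**The case against.** Five points can be made for leaving the plan as it is.

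- **Zero is not inevitable.** The protocol's only gloss on the rule is weekly, and with full diaries kappa then falls without vanishing. This stands. A reader might infer that kappa must be zero by construction; the documents do not support that, because they never say how the rule applies to 14 nights.
- **The alternative set is also selected.** Actiwatches are dispensed at Visit 1, after the sleep problem has been verified on the pre-Visit 1 diary or, for children with documented sleep-hygiene training, on parent report. This stands too. Without that screening, the Beta(2,2), 80% model gives 0.62 (proportion) and 0.60 (weekly). With it, the attainable values are about 0.4 to 0.5. The unscreened figures overstate what the fix recovers.
- **The table would not look like disagreement.** A reader might infer that it would show the diary contradicting actigraphy. Under the proportion reading with 14 nights, Beta(2,2) and no Visit 1 check, only about 1.4% of selected children are actigraphy responders at 80% nightly agreement and 0.1% at 90%. Nearly all fall in the joint non-responder cell. With 120 children, the chance that actigraphy finds none is 0.986^120 = 18% or 0.999^120 = 89%, and kappa is then undefined. So the counts would reveal an empty margin; the kappa and its test would still be uninformative.
- **A general rule may catch it.** SAP Section 16 produces tables only where the data are sufficient. That could suppress a degenerate table, but it does not deal with a truncated margin or answer the agreement question.
- **It is one supportive statistic.** Agreement is mainly assessed by Bland-Altman methods on continuous parameters at Visits 2 and 4. This is correct and sets the severity.

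**Conclusion.** The point holds at low severity. As planned, the Visit 2 responder kappa is computed in children chosen by the diary being compared. The result is zero, undefined or lowered, depending on an unstated reading of the 3-out-of-5-nights rule and on diary completeness. That no eligible child can be a diary responder under the proportion reading, or with five diaries a week, needs no assumption beyond the entry rule being followed. The size of the loss under the weekly reading rests on the simulation inputs above and is an illustration, not a forecast.

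Kappa and its test against zero would partly reflect selection rather than measurement disagreement. It would be wrong to conclude that the diary endpoint or the wider agreement analysis is undermined: this kappa feeds no primary or secondary endpoint, and the TST model and the Bland-Altman analyses do not use the responder classification.

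**What to change.** Run Table 14.2.19 on all enrolled children who have both run-in diary and run-in actigraphy data, including those not randomised after run-in. This is the set that Table 14.2.13.2 draws on. The data should exist: run-in diaries must be entered at Visit 2 for the eligibility check, Actiwatches are collected then, and screen failures go into the eCRF (Protocol 8, 8.5 and 12.1).

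In SAP 11.7, state how 3 out of 5 nights applies to the 14-night window for each source. Add a footnote that this set was still screened for a sleep problem at Visit 1, so the diary margin remains partly restricted, and that kappa is not reported if either source yields no responders.

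Adding Visit 4 is optional. Its diary was not used for selection, but the item is defined as a baseline comparison.

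The cost is a population label, one clarifying sentence and a footnote, with no new data collection.

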11.8 Correlation between Sleep and Nap Diary and Actigraphy versus Daytime Endpoints

Scatterplots will be presented for selected sleep parameters collected via the Sleep and Nap Diary and actigraphy against CSDI, CGAS and SDQ Total score as follows:

- SND TST versus CSDI
- SND TST versus CGAS
- SND TST versus SDQ Total Score
- SND Sleep Latency versus CSDI
- SND Sleep Latency versus CGAS
- SND Sleep Latency versus SDQ Total Score
- SND WASO versus CSDI
- SND WASO versus CGAS
- SND WASO versus SDQ Total Score
- Actigraphy TST versus CSDI
- Actigraphy TST versus CGAS
- Actigraphy TST versus SDQ Total Score
- Actigraphy Sleep Latency versus CSDI
- Actigraphy Sleep Latency versus CGAS
- Actigraphy Sleep Latency versus SDQ Total Score
- Actigraphy WASO versus CSDI
- Actigraphy WASO versus CGAS
- Actigraphy WASO versus SDQ Total Score

Spearman's rank correlations will be calculated and presented on the scatterplot for each correlation. In addition, the null hypothesis of zero correlation will be tested.

12 Safety

Subjects will be classified and summarized by actual treatment.

Safety will be assessed using TESS, AEs, vital signs, BMI and physical development data.

12.1 Treatment Exposure

Details of study drug compliance, dose modifications and dose increases will be listed.

The time on treatment will be listed and summarized descriptively.

Time on treatment (days) in DB Phase = Last dose date of DB phase – first dose date of DB phase +1

Time on treatment (days) in OL Phase = Last dose date of OL phase – first dose date of OL phase +1

Time on active treatment (days) = Last dose date of active treatment – first dose date of active treatment +1

The number of subjects having a decrease in dose or an increase in dose will be tabulated by visit. % compliance will be summarized descriptively.

The dosage achieved (2/5/10mg) will be tabulated by scheduled visit and the maximum dose achieved will also be tabulated.

12.2 Treatment Emergent Signs and Symptoms

TESS are recorded throughout the study. At Visit 1, the TESS questionnaire is completed and the information is used to assess medical history. All symptoms that are score of 1 or more will be recorded in the medical history. At Visit 2 and all subsequent visits thereafter, the TESS questionnaire will be used to report all treatment-emergent signs and symptoms that may have occurred since Visit 1. A given sign and symptom will be reported as a corresponding AE if the sign or symptom is a new symptom or if there is an increase in severity of an existing symptom from the first visit (i.e., Visit 1). If a specific symptom has the same score or lower from Visit 1, AEs will not be reported.

A frequency table of TESS results will be presented by sign/symptom and scheduled visit for the thirteen hypothesized events.

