7.4 BLINDING

The initial 2-week SB placebo run-in period of this study is designed as a SB period with the patients blinded as to what study drug they will receive. All patients will receive placebo during the run-in period. The run-in period will be followed by 13 weeks of double-blind treatment, where the Investigator and the patient will be blinded to treatment allocation. Patients will be randomized using a 1:1 ratio to receive either Circadin® 2 mg (2 minitabets each containing 1 mg of Circadin®) or placebo (2 minitabets containing 1 mg of placebo). The placebo will have the same appearance as Circadin®. After 3 weeks of study, if dose modification is deemed necessary, patients will receive increased doses in the same manner (5 minitabets containing 1 mg of Circadin® or placebo). The randomization scheme will be designed to ensure that patients requiring dose modification will continue receiving the same treatment (Circadin® or placebo).

Except in an emergency, the blind should not be broken until all completed eCRFs are received by Data Management and the database is locked.

All sites will receive unblinding envelopes to facilitate emergency unblinding if needed.

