At Visit 1, the TESS questionnaire ([Appendix 5](#)) is completed and the information is used to assess medical history. All symptoms that are score of 1 or more should be recorded in the medical history as it will serve us throughout the study as a baseline to see if a symptom was worsen or not. At Visit 2 and all subsequent visits thereafter, the TESS questionnaire is used to report all treatment-emergent signs and symptoms that may have occurred since Visit 1. As instructed in [Appendix 5](#), a given sign and symptom is to be reported as a corresponding AE if a score of 1 or above is selected, and if the sign or symptom is a new symptom or if there is an increase in severity of an existing symptom from the first visit (i.e., Visit 1). If a specific symptom has the same score or lower from Visit 1 AEs should not be reported.

Adverse events are also to be reported on the appropriate page of the patient's eCRF.

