9.3 Baseline Derivation

For all efficacy and safety variables, the baseline value will be calculated as the last recorded value prior to the start of randomized treatment.

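### TESS adverse events are judged against Visit 1, before the placebo run-in, although the SAP sets the safety baseline immediately before randomized treatment

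*SAP*

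**What the plan says.** SAP 12.2 uses TESS at Visit 1 to build the medical history. After that, "the TESS questionnaire will be used to report all treatment-emergent signs and symptoms that may have occurred since Visit 1". A symptom is an AE if it is new or more severe than at Visit 1, and otherwise it is not: "If a specific symptom has the same score or lower from Visit 1, AEs will not be reported". Protocol 11.1.1 gives sites the same instruction ("If a specific symptom has the same score or lower from Visit 1 AEs should not be reported") and says of the Visit 1 record that "it will serve us throughout the study as a baseline to see if a symptom was worsen or not". The TESS form in Protocol Appendix 5 repeats the comparison with the first visit and sets the trigger at a score of 1 or more on a 0 to 3 scale.

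Between Visit 1 and Visit 2 comes the two-week run-in. Protocol 7.4: "All patients will receive placebo during the run-in period".

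SAP 9.3 states, for all efficacy and safety variables, that "the baseline value will be calculated as the last recorded value prior to the start of randomized treatment". Protocol Table 5-2 and Section 8.5 schedule TESS at Visit 2, so that value is the Visit 2 score. Physical-examination AEs already take Visit 2 as their baseline (Protocol 11.5, SAP 12.8.2).

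SAP 12.3 tabulates treatment-emergent AEs for the double-blind and open-label phases. It neither defines treatment-emergent nor says how an AE is assigned to a phase.

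**The concern.** The plan has two safety baselines and does not explain the difference. The TESS baseline lies before a period in which every child takes placebo. For children who needed it, it also follows directly on withdrawal of prohibited medication, so a Visit 1 score may not describe the child at randomization.

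Two kinds of event are affected. A symptom that has gone by Visit 2 and comes back on double-blind treatment may go unreported as an AE. A symptom that begins on run-in placebo is recorded as an AE and may later be read as emerging on randomized treatment. The 13 items include somnolence, fatigue, increased excitability and mood swings. Protocol 7.3.1 and 7.3.2 themselves single out daytime fatigue and behavioral change as effects to watch for, so these are items on which a reader would want a clean comparison.

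**Working it through.** There is no stated figure to reproduce. The check enumerates what the rule does to each possible set of scores. These are counts of score patterns, not of children.

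**Inputs.** Score 0 to 3 at Visit 1 (V1), Visit 2 (V2) and one later visit (L), giving 4 × 4 × 4 = 64 patterns.
- Rule as written (SAP 12.2, Protocol 11.1.1, Appendix 5): AE if L ≥ 1 and L > V1.
- Rule with the SAP 9.3 baseline: AE if L ≥ 1 and L > V2.

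**All 64 patterns.**
- AE under both rules: 14.
- AE only against Visit 2, so missed as written (V2 < L ≤ V1): 10.
- AE only against Visit 1, so no worse than just before randomization (V1 < L ≤ V2): 10.
- AE under neither: 64 − 14 − 10 − 10 = 30.

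Status changes for 10 + 10 = 20 of the 64.

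**Present at Visit 1, cleared at Visit 2, back later** (V1 = 1 to 3, V2 = 0, L = 1 to 3): 3 × 3 = 9 patterns, written V1-V2-L.
- Not AEs as written: 1-0-1, 2-0-1, 2-0-2, 3-0-1, 3-0-2, 3-0-3 (6 patterns).
- AEs as written, because the return exceeds the Visit 1 score: 1-0-2, 1-0-3, 2-0-3 (3 patterns).

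**Worsening during the run-in** (V2 > V1): 6 score pairs (0-1, 0-2, 0-3, 1-2, 1-3, 2-3). All 6 are recorded as AEs at Visit 2.

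**Can run-in AEs reach the treatment-emergent tables?** Set side by side:
- Protocol 11.1.1 requires all AEs after Visit 1 to be reported.
- Protocol 12.1 counts an event as treatment-emergent from the first dose of study medication, without saying whether run-in placebo qualifies.
- Protocol 8.3 has the run-in supply dispensed at Visit 1 as study drug.
- SAP 10.6 assigns concomitant medications to phases, with the double-blind phase running from Visit 2 to Visit 4. SAP 12.3 has no counterpart for AEs.

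Nothing in the SAP excludes run-in events. An onset-date rule alone would leave a gap, because Protocol 11.1.2 makes each change in severity a separate event. Read literally, a symptom scored 0-2-1 at Visits 1, 2 and 3 yields a new record at Visit 3, although the child is better than at randomization.

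**Effect of suppression on the comparison.** Suppose both arms lose the same fraction of events. With illustrative rates of 2 and 1 and 10% lost in each arm, the ratio is (0.9 × 2)/(0.9 × 1) = 2.0, unchanged. The difference is 1.8 − 0.9 = 0.9 instead of 1.0.

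**The case against.** The strongest reply is that the Visit 1 reference is a deliberate collection rule, stated consistently in the protocol, the TESS form and the SAP. It fits the protocol's position that ordinary fluctuation of a pre-existing condition need not be an AE. It applies equally to both arms, and both visits precede randomization, so it favors neither arm. The AE analysis is descriptive. Much of this stands. It does not reconcile SAP 12.2 with SAP 9.3, and it does not supply the missing definition of a treatment-emergent AE.

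A reader might infer that returning symptoms are never counted. That goes too far. Three of the nine patterns are AEs, and any symptom present at a visit appears in the by-visit TESS table (Table 14.3.2.1) and in the TESS listing. What that table lacks is change from Visit 2. The relatedness, severity and discontinuation summaries draw on AEs, not on TESS scores.

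A reader might also infer that run-in events are counted as double-blind events, so that the comparison is biased towards no difference. One could then take the run-in as 2 of the 15 weeks since Visit 1 and shrink a true rate ratio of 2.0 to (13 × 2 + 2 × 1)/15 = 1.87. The documents do not support this. Only the recording of run-in events is certain. The tables are by phase, there is no run-in table, and SAP 12.1 times double-blind exposure from the first dose of that phase. If run-in events stay out, dilution from this source is zero. Suppression at an equal rate in both arms leaves the ratio unchanged.

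**Conclusion.** The inconsistency is real and should be corrected. Followed as written, the plan does not report as AEs those symptoms that clear in the run-in and return on double-blind treatment at or below the Visit 1 score (6 of 9 such patterns). It also leaves open whether events arising on run-in placebo count as treatment-emergent. The consequence is missed or misattributed events and possibly a smaller absolute difference between arms.

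The size cannot be derived. It depends on how often symptoms are present at Visit 1, clear by Visit 2 and return, and the documents give none of these frequencies. For the same reason, no percentage of affected children can be defended. A bias in the rate ratio, or in favor of one arm, is not shown. The conclusion rests on reading SAP 9.3 as covering TESS, which its reference to all safety variables supports, and on TESS being completed at Visit 2 as scheduled.

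**What to change.** - **SAP 12.2:** add a shift table by treatment group showing worsening from the Visit 2 TESS score for the 13 items. State that the Visit 1 comparison governs site reporting, and that the analysis baseline is the one in SAP 9.3.
- **SAP 12.3:** define double-blind treatment-emergent AEs as events with onset or worsening after the first randomized dose, and report run-in AEs separately.

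The cost is one extra table and one derivation rule. The Visit 2 and later scores are already collected, so no new data are needed. There is a limit to what this recovers: sites following the protocol will not have entered the suppressed symptoms as AEs. These can be recovered as TESS scores, but not as full AE records with onset date and causality.
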